12.1.5.1 Permitted concomitant therapy requiring caution and/or action

CCI

CCI

CCI

12.2 Cohort B1: INE963 + Cipargamin

Cohort B1 will start after the completion of Cohort A1. Cohort B1 will evaluate the use of INE963 and KAE609 (cipargamin) in combination vs the SoC (Coartem) in patients with uncomplicated *P. falciparum* malaria.

INE963 background information can be found in [Section 12.1.1](#).

12.2.1 Cipargamin Background

Cipargamin, a spiroindolone, represents a new class of potent, fast-acting, schizonticidal anti-malarial. It appears to exert its antiplasmodial activity through deregulation of Na⁺ homeostasis in the parasite cytosol through inhibition of a P-type nonSERCA ATPase, PfATP4.

CCI

CCI

12.2.2 Cohort B1 Study Design

In Cohort B1, INE963 and cipargamin will be evaluated as combination therapy vs the SoC (Coartem).

Table 12-9 Treatment Arm(s) for Cohort B1 – INE963 + Cipargamin

Arm Title	INE963 + Cipargamin	Standard of Care
Arm Type	Experimental	Standard of Care control - Coartem
Arm Description	CCI	BID for 3 days (at the following time points: 0, 8, 24, 36, 48, and 60 hours) and must be received with a standard meal or drink rich in fat, as per label.

12.2.3 Cohort B1 Sample Size

CCI

CCI

CCI

12.2.6 Cohort B1 Study Population and Special Restrictions

Additional Exclusion Criteria

Patients meeting any of the following criteria are not eligible for inclusion in this study:

Women of child-bearing potential, defined as all women physiologically capable of becoming pregnant, unless they are using highly effective methods of contraception during dosing and for 5 half-lives. Highly effective contraception methods include:

- Total abstinence when this is in line with the preferred and usual lifestyle of the subject. Periodic abstinence (e.g., calendar, ovulation, symptothermal, post-ovulation methods) and withdrawal are not acceptable methods of contraception.
- Female bilateral tubal ligation, female sterilization (have had surgical bilateral oophorectomy with or without hysterectomy), or total hysterectomy at least six weeks before taking investigational drug. In case of oophorectomy alone, only when the reproductive status of the woman has been confirmed by follow up hormone level assessment.
- Male sterilization (at least 6 months prior to screening). For female patients on the study, the vasectomized male partner should be the sole partner for that patient.

- Use of oral (estrogen and progesterone), injected, or implanted hormonal methods of contraception or placement of an intrauterine device (IUD) or intrauterine system (IUS) or other forms of hormonal contraception that have comparable efficacy (failure rate < 1%), for example hormone vaginal ring or transdermal hormone contraception. Coartem/Riamet may reduce the effectiveness of hormonal contraceptives. Therefore, patients randomized to Coartem using oral, transdermal patch, or other systemic hormonal contraceptives should be advised to use an additional non-hormonal method of birth control.
- In case of use of oral contraception, women should have been stable on the same pill for a minimum of 3 months before taking investigational drug.

In addition to the below special restriction(s) specific to cipargamin, the special restrictions specific to INE963 can be found in [Section 12.1.5](#).

- Patients are advised to use commonly recommended precautions when in the sun (e.g., sunscreen, hat, protective clothing) from first dosing until study completion evaluation.

12.2.6.1 Permitted concomitant therapy requiring caution and/or action

[figure not shown]
A large, bold, red watermark consisting of the letters 'CCI' is displayed on a solid black rectangular background. The letters are stylized with a slight gap in the middle of each letter.

CCI

CCI

12.2.8 Cohort B1 PK/PD and Biomarker Assessments

CCI

12.2.9 Cohort B1 Compound Specific Assessments

CCI

12.3 Cohort B2: KLU156 + cipargamin

CCI

12.3.1 KLU156 Background

CCI

CCI

12.3.2 Cohort B2 Study Design

CCI

CCI

12.3.3 Cohort B2 Sample Size

CCI

12.3.4 Cohort B2 Dose Rationale

12.3.4.1 Rationale for choice of KAE609 as combination drug with KLU156

Selection of cipargamin as partner drug with KLU156 for Cohort B2:

[illegible]

12.3.4.2 Rationale for dose/regimen and duration of treatment

[illegible]

CCI
[Redacted text block]

12.3.5 Cohort B2 Risks and Benefits

Risks and benefits relating to cipargamin

Risks and benefits relating to cipargamin can be found in [Section 12.2.5](#).

KLU156 and cipargamin IMP Related Risk

Against the background of the COVID-19 pandemic, the potential risk of a patient developing COVID-19 has been considered in terms of the risk-benefit evaluation. The mode of action of this anti-malarial agent has been considered alongside available pre-clinical and clinical data (including class effects) and it is considered that a patient would not be at increased risk of either becoming infected with severe acute respiratory syndrome coronavirus 2 (SARS-CoV-2; the virus that causes COVID-19) or experiencing a more severe illness. That is, this agent has no known immunomodulatory effect that would confer an increased risk to patients enrolled in the study.

Related Risk and Benefits Related to KLU156 (KAF156 i.e., ganaplacide/LUM-SDF i.e., lumefantrine-SDF)

CCI
[Redacted text block]

CCI

A large black rectangular redaction box covers the majority of the page content below the header and above the section title. The word "CCI" is printed in red at the top left of this redacted area.

Risks and benefits relating to cipargamin and KLU156 co-administration

CCI

A large black rectangular redaction box covers the majority of the page content below the section title. The word "CCI" is printed in red at the top left of this redacted area.

12.3.6 Cohort B2 Study Population and Special Restrictions

Additional Exclusion Criteria

Patients meeting any of the following criteria are not eligible for inclusion in this study:

Women of child-bearing potential, defined as all women physiologically capable of becoming pregnant, unless they are using highly effective methods of contraception during dosing and for 5 half-lives. Highly effective contraception methods include:

- Total abstinence when this is in line with the preferred and usual lifestyle of the subject. Periodic abstinence (e.g., calendar, ovulation, symptothermal, post-ovulation methods) and withdrawal are not acceptable methods of contraception.
- Female bilateral tubal ligation, female sterilization (have had surgical bilateral oophorectomy with or without hysterectomy), or total hysterectomy at least six weeks before taking investigational drug. In case of oophorectomy alone, only when the reproductive status of the woman has been confirmed by follow up hormone level assessment.
- Male sterilization (at least 6 months prior to screening). For female patients on the study, the vasectomized male partner should be the sole partner for that patient.
- Use of oral (estrogen and progesterone), injected, or implanted hormonal methods of contraception or placement of an intrauterine device (IUD) or intrauterine system (IUS) or other forms of hormonal contraception that have comparable efficacy (failure rate < 1%), for example hormone vaginal ring or transdermal hormone contraception. Coartem/Riamet may reduce the effectiveness of hormonal contraceptives. Therefore, patients randomized to Coartem using oral, transdermal patch, or other systemic hormonal contraceptives should be advised to use an additional non-hormonal method of birth control.
- In case of use of oral contraception, women should have been stable on the same pill for a minimum of 3 months before taking investigational drug.

12.3.6.1 Permitted concomitant therapy requiring caution and/or action

CCI

[REDACTED]

CCI

CCI

CCI

CCI

12.3.7 Cohort B2 Study Treatment

A large, bold, red watermark consisting of the letters 'CCI' is positioned in the upper left quadrant of the page. The background of the entire page is black, and the watermark is the only visible text in this area.

- Patients should be instructed to swallow whole capsules and not to chew or open them.
- Each subject's mouth must be checked to ensure that the medication was swallowed.
- Subjects should be administered KLU156 under fed conditions with light meal (estimate of 100-300 calories, 5-10 g of fat). Cipargamin can be administered irrespective of food intake
- In case of Coartem, medication should be followed by a normal diet or a drink rich in fat (including broth, sweetened condensed milk, etc.) within 30 min of dosing as per label.

- In case that vomiting occurs
 - KLU156+ cipargamin: In the case that the patient vomits within 1 hour of intake a replacement dose will be given to the patient and the investigator or designee will notify IRT. If the replacement dose is vomited, the patient has to be given Coartem as rescue medication or another suitable rescue medication as per local guidelines.
 - Coartem: In the case that the patient vomits within 1 hour of intake a replacement dose will be given to the patient and the investigator or designee will notify IRT. If the replacement dose is vomited, the patient has to be given non-lumefantrine standard of care.

12.3.8 Cohort B2 PK/PD and Biomarker Assessments

CCI

CCI

Pharmacokinetic assessments will be performed as described in [Section 8.7](#). In addition to PK parameters mentioned in [Section 8.7](#), C_{168h} (concentration at 168h) and AUC_{0-168h} (Area under the plasma concentration time curve from zero to 168h) will be determined using the actual recorded sampling times and non-compartmental method(s) with Phoenix WinNonlin (Version 6.4 or higher).

**List of figures**

Figure 1-1	Study design .....	9
------------	--------------------	---

---

List of abbreviations

---

AE	Adverse event
ACPR	Adequate clinical and parasitological response
ATC	Anatomical Therapeutic Classification
AUC	Area Under the Curve
BID	bis in diem/ Twice a day
CRF	Case Report Form
CSR	Clinical Study Report
CTC	Common Toxicity Criteria
CTCAE	Common Terminology Criteria for Adverse Events
DBL	Data base lock
DMS	Document management system
eCRF	Electronic Case Report Form
ETF	Early treatment failure
FAS	Full Analysis Set
IA	Interim Analysis
LCF	Late clinical failure
LPF	Late parasitological failure
MedDRA	Medical Dictionary for Drug Regulatory Affairs
o.d.	Once Daily
PK	Pharmacokinetics
Qd	Qua'que di'e / once a day
RAS	Randomized analysis set
SAF	Safety analysis set
SAP	Statistical Analysis Plan
SAS	Statistical Analysis System
SD	Single dose
SDF	Single dose formulation
SoC	Standard of care
SOC	System Organ Class
TFLs	Tables, Figures, Listings
WHO	World Health Organization

---

## 1 Introduction

This Statistical Analysis Plan (SAP) provides detailed statistical methodology for the analysis of data from study CADPT13A12201 that will be presented in the Clinical Study Report(s) (CSR). This version of the SAP is based on protocol version 03 released 20-Mar-2024.

The output shells accompanying this document can be found in the Tables, Figures and Listings (TFL) shells document.

All changes to the planned analysis described in this document required before or after database lock will be made through an amendment or addendum, respectively.

Any data analysis carried out independently by the investigator should be submitted to Novartis before publication or presentation.

The analysis will be performed by Novartis and carried out using SAS, Version 9.4 or higher.

### 1.1 Study design

This is a Phase 2, multi-part, multi-center, open-label platform study including CCI

This platform design allows the potential to investigate multiple therapies in the context of a single disease. Each anti-malarial agent entered in the trial at a given time will follow the same design as outlined in Parts A, B, and C. More than one Part A, Part B, and Part C cohort can be conducted at the same time. In addition, Part A, Part B, and Part C cohorts can be conducted at the same time.

CCI

CCI

**Part A** is the open-label, randomized, multi-arm monotherapy part of this Phase 2 study evaluating a single oral administration of an anti-malarial agent at 3 parallel dose levels followed by optional adaptive sequential dose level(s).

CCI

**Part B** is the open-label, randomized, two-arm combination therapy part of this Phase 2 study evaluating a single oral dose of up to three anti-malarial agents as a loose combination vs. standard of care (SoC), Coartem in adult and adolescent patients.

CCI

CCI

**Part C** is the open-label, randomized, two-arm combination therapy part of this Phase 2 study evaluating a single oral dose of up to three anti-malarial agents as a loose and/or fixed combination vs. SoC, Coartem, in children aged 2 to < 12 years.

CCI

## 1.2 Study objectives, endpoints and estimands

The study objectives and endpoints are described in [Table 1-1](#).

**Table 1-1 Objectives and related endpoints**

Objective(s)	Endpoint(s)
Primary objective(s)	Endpoint(s) for primary objective(s)
CCI	
Secondary objective(s)	Endpoint(s) for secondary objective(s)
Part A:	

CCI

	

PCR-corrected and uncorrected adequate clinical and parasitological response (ACPR) at Day 29 (i.e., 28 days post-dose)

Parts B & C:	

To assess the parasite clearance time (PCT) of oral combinations of anti-malarial agents versus the standard of care (SoC) in patients with uncomplicated P. falciparum malaria

	

Parasite clearance time (hours) up to Day 7

CCI

	

CCI

Parts A, B, & C:	

To characterize PK of each anti-malarial agent administered orally as monotherapy [Part A]

	

PK parameters such as Cmax, Tmax, and wherever possible AUC0-t, AUClast, AUCinf, T1/2, CI/F, VI/F

Objective(s)	Endpoint(s)
and/or as combination therapy [Parts B and C] in patients with uncomplicated P. falciparum malaria	

 
To assess the safety and tolerability of each anti-malarial agent administered orally as monotherapy [Part A] and/or as combination therapy versus SoC [Parts B and C] in patients with uncomplicated P. falciparum malaria
 
	
 
Adverse events, vital signs, ECG findings, safety laboratory assessments including chemistry, hematology, and urinalysis results up through EOS
 

Exploratory objective(s)	Endpoint(s) for exploratory objective(s)

CCI

### 1.2.1 Primary estimand(s)

CCI

CCI

CCI

### 1.2.2 Secondary estimand(s)

CCI

- The key secondary estimand attributes in Part A are described as identical to the attributes in the primary estimand in Parts B and C, except in Part A:
  - **Population** is adults who receive an anti-malarial agent fully administered
  - CCI [REDACTED]
  - **Summary measure** is PCR-corrected ACPR rate by treatment group.

CCI

- The key secondary estimand attributes in Parts B and C are described as identical to the attributes in the primary estimand in Part A, except in Parts B and C:
  - **Population** is adult or adolescent patients (Part B) and pediatric patients (Part C)
  - **Treatment of interest** is anti-malarial agent administered in combination with other antimalarial agents or SoC.

### 1.2.3 Other secondary estimand

CCI

The other secondary estimand is described by the following attributes:

1. **Population:** Adult (Part A)/Adult or adolescent (Part B)/Pediatric (Part C) patients with acute uncomplicated *P. falciparum* malaria.

2. **Variable:** A binary outcome indicating the patient did not take concomitant medication with anti-malarial activity prior to Day 29 and has achieved uncorrected ACPR at Day 29.
3. **Treatment of interest:** anti-malarial agent administered as monotherapy (Part A)/in combination with other anti-malarial agents or SoC (Parts B and C) regardless of study discontinuation or non-compliance.
4. **CCI**
5. **Summary measure:** Uncorrected ACPR rate by treatment group (Part A)/difference in proportion between the combination therapy and SoC (Parts B and C).

The estimand strategy for this estimand is a mixture of treatment policy (for discontinuation or non-compliance) and composite strategy (for non-study anti-malarial agents).

## 2 Statistical methods

### 2.1 Data analysis general information

Unless otherwise noted, by default all outputs will be presented by cohort (e.g. A1, B1, B2, C2) and treatment group within each cohort. Data from common treatment groups and/or doses may be pooled at a later time. *In the following sections, “by cohort and treatment group” is thus removed as it applies to all outputs.*

#### 2.1.1 General definitions

**CCI**

The following treatment group names will be used in statistical analyses and outputs:

**CCI**

Part B1: INE963+Cipargamin, Coartem

Parts B2 & C2: KLU156+Cipargamin, Coartem

#### Date of first administration of study treatment

The date of first administration of study treatment is defined as first date when a nonzero dose of study treatment is administered and recorded on the Dosage Administration Record eCRF. The date of first administration of study treatment is also referred to as *start of study treatment*.

The date of last administration of study treatment is defined as last date when a nonzero dose of study treatment is administered and recorded on the dose administration eCRF.

#### Study day

Study day 1 for all assessments is taken to be the start of study treatment.

The study day for all assessments will be calculated as follows:

1. If date of assessment occurred on or after the start of study treatment, then  
 $\text{Study day} = \text{Date of assessment} - \text{Start of study treatment} + 1.$
2. If date of assessment occurred before the start of study treatment, then  
 $\text{Study day} = \text{Date of assessment} - \text{Start of study treatment}.$

The study day will be displayed in the data listings. If an event starts before the reference start date, the study day displayed on the listing will be negative.

### Baseline

For safety evaluations, the last available assessment on or before the start date of study treatment is taken as “baseline” assessment. In case time of assessment and time of treatment start is captured, the last available assessment before the treatment start date/time is used for baseline.

For safety parameters (e.g., ECGs), where the study requires multiple replicates per time point, the average of these measurements will be calculated (if not already available in the database) before determining baseline. The associated time will be the time of the last replicate.

### On-treatment assessment/event

The overall observation period will be divided into two mutually exclusive segments:

1. ***Pre-treatment period:*** from day of patient’s informed consent to before date of first administration of study treatment
2. ***On-treatment period:*** from date of first administration of study treatment (study day 1) onwards.

*Note:* If dates are incomplete in a way that clear assignment to pre- or on-treatment period cannot be made, then the respective data will be assigned to the on-treatment period.

Safety summaries (tables, figures) include only data from the on-treatment period with the exception of baseline data which will also be summarized where appropriate (e.g., change from baseline summaries). In particular, summary tables for AEs will summarize only on-treatment events, with a start date during the on-treatment period (***treatment-emergent*** AEs).

The image shows a large, bold, red logo consisting of the letters 'C', 'C', and 'I' in a stylized, sans-serif font. The logo is positioned on the left side of a solid black rectangular background that occupies the bottom third of the page.

CCI

Note: The first day of treatment is defined as Day 1 while the day prior to the first day of treatment is defined as Day -1. Compared to [WHO \(2015\)](#) which defined Day 0 as the first day of study treatment, days after treatment are 1 day greater. For example, Day 29 corresponds to Day 28 by [WHO \(2015\)](#).

CCI

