Each cohort will include a screening period [REDACTED]. Eligible patients will be dosed on Day 1 and remain at the site for inpatient follow-up for at least 3 days. Safety, efficacy, and PK assessments will be performed for the 3 days. Patients may remain inpatient longer at the investigator's discretion. [REDACTED]

[REDACTED] A safety follow-up call will be performed on Day 31 for Part A. The visit structure at each cohort level for Parts A and B of the study is shown in [Figure 3-2](#). Cohort-specific study designs are outlined in [Section 12](#).

For a detailed outline of the core safety and other assessments, please refer to the assessment schedule in [Table 8-1](#). Cohort-specific assessments are outlined in [Section 12](#).

Figure 3-2 Study Design - Cohort Level View

Part A: Monotherapy

[REDACTED]

Safety assessments will include physical examinations, triplicate ECGs, vital signs, standard clinical laboratory evaluations (hematology, blood chemistry, and urinalysis), adverse event and serious adverse event monitoring.

[REDACTED]

Multiple cohorts, each with a different anti-malarial agent, may be added. Each new anti-malarial agent evaluated will follow the same design.

Part B: Combination Therapy

In Part B, patients will be randomized to receive a single oral dose of a combination of up to three anti-malarial agents or the standard of care (Coartem). See [Figure 3-1](#). Specific randomization ratios for each cohort will be specified in [Section 12](#).

Doses for agents in Part B will be selected based on review by the Sponsor and the DMC of PK, safety, and efficacy data from Part A. Safety, efficacy and/or PK data may be evaluated in the first few patients (approximately 6 in each arm) in Part B and reviewed by the Sponsor for

safe use of combination in patients. The dose(s) may be adjusted based on these data in order to meet the desired exposure or to mitigate potential safety risks.

Safety assessments will include physical examinations, triplicate ECGs, vital signs, standard clinical laboratory evaluations (hematology, blood chemistry, and urinalysis), adverse event and serious adverse event monitoring.

CCI

Multiple cohorts with different anti-malarial agents may be added. Each new anti-malarial agent combination evaluated will follow the same design.

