6.1.3 Treatment duration

For Part A, the planned duration of treatment is 1 day.

For Part B, the planned duration of treatment is 1 day for patients randomized to the active investigational medicinal products administered as a loose combination or 3 days for patients randomized to the standard of care arm. Patients may be discontinued from SoC treatment earlier at the discretion of the investigator or the patient.

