6.8.3 Rescue medication

The following rescue medications may be used per investigator discretion:

- Coartem (Artemether-Lumefantrine)
or
- Other local standard anti-malarial agent

In Part A, Coartem (artemether-lumefantrine) or other local standard anti-malarial agent per investigator discretion will be administered on Day 29 in all patients in Part A of the study. If Coartem or other local standard anti-malarial agent is used as rescue medication prior to Day 29 due to treatment failure (see [Section 8.3.4](#)), then another course is not needed at Day 29.

In Part B, Coartem or other local standard anti-malarial agent per investigator discretion will be used as rescue medication only for patients not randomized to the SoC in Part B if they meet the treatment failure criteria (see [Section 8.3.4](#)). An alternative rescue medication should be used for patients assigned to the SoC arm if they met treatment failure criteria.

Although the use of the above rescue medication is allowable at any time during the study when there is treatment failure in Part A or B, the use of rescue medication should be used at the discretion of the PI following the failure criteria as outlined in [Section 8.3.4](#). The date and time of rescue medication administration as well as the name and dosage regimen of the rescue medication must be recorded.

7 Discontinuation of study treatment and participant discontinuation/withdrawal

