9.4.2 Safety endpoints

For all safety analyses, the SAF will be used. All listings and tables will be presented by single anti-malarial agent, study part, and treatment group.

Safety summaries (tables, figures) include all post treatment data with the exception of baseline data which will also be summarized where appropriate (e.g., change from baseline summaries). In particular, summary tables for adverse events (AEs) will summarize using all post-treatment events, with a start date on or after the first treatment (treatment-emergent AEs).

Adverse events

All information obtained on adverse events will be displayed by each single anti-malarial agent, study part, treatment group and patient.

The number (and percentage) of patients with treatment emergent adverse events (events started after the first dose of study medication or events present prior to start of treatment but increased in severity based on preferred term) will be summarized in the following ways:

- by each single anti-malarial agent, study part, treatment group, primary system organ class and preferred term.
- by each single anti-malarial agent, study part, treatment group, primary system organ class, preferred term and maximum severity.
- by each single anti-malarial agent, study part, treatment group, Standardized MedDRA Query (SMQ) and preferred term.

Separate summaries will be provided for study medication related adverse events, death, serious adverse events, other significant adverse events leading to discontinuation, and adverse events leading to dose interruption in the SoC of Part B.

A patient with multiple adverse events within a primary system organ class is only counted once towards the total of the primary system organ class.

Vital signs

All vital signs data will be listed by single anti-malarial agent, study part, treatment group, patient, and visit/time and if ranges are available, abnormalities (and relevant orthostatic changes) will be flagged. Summary statistics will be provided by single anti-malarial agent, study part, treatment group, and visit/time.

12-lead ECG

PR, QRS, QT, QTcF, and RR intervals will be obtained from 12-lead ECGs for each patient during the study. ECG data will be read and interpreted (centrally).

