## 2.7 Safety analyses

For all safety analyses, the Safety set will be used. Safety summaries include data from the on-treatment period with the exception of baseline data which will be summarized where appropriate (e.g., change from baseline summaries). In particular, summary tables for AEs will summarize treatment-emergent AEs (i.e. with a start date on or after the first treatment).

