### **2.7.3 Laboratory data**

Descriptive statistics will be generated for all clinical laboratory tests performed (actual values and changes from baseline) for three groups of laboratory tests (hematology, clinical chemistry and urinalysis).

Shift tables using the low/normal/high classification will be used to compare baseline to the worst post-baseline value.

Summary with frequency and percent of patients with liver related events (based on AST, ALT, and Total Bilirubin) using the Novartis standard table will be provided.

Boxplots for hematology and biochemistry parameters will be provided.

Listing for patients with lab values outside the normal range (per normal ranges in the source dataset) will be provided. If there is any abnormal lab value for a patient, all measurements of this lab value for the patient will be presented with the abnormal values flagged.

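### The open-ended on-treatment period does not separate safety data collected after a non-study antimalarial, and the overlap is largest in patients rescued early, so in the less effective arms

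*SAP*

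**What the plan says.** The SAP (2.1.1, On-treatment assessment/event) divides observation into two mutually exclusive segments, pre-treatment and on-treatment. The second runs "from date of first administration of study treatment (study day 1) onwards", with no closing date. The same paragraph states that "Safety summaries (tables, figures) include only data from the on-treatment period", apart from baseline values where appropriate, and SAP 2.7 repeats the rule. Protocol 9.4.2 agrees: "summary tables for adverse events (AEs) will summarize using all post-treatment events, with a start date on or after the first treatment". Laboratory shift tables "compare baseline to the worst post-baseline value" (SAP 2.7.3). Notable ECG values and newly occurring notable vital signs are counted over the same period (SAP 2.7.4).

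On treatment, Protocol 6.1.3 states: "For Part A, the planned duration of treatment is 1 day". Protocol 6.8.3 then says that Coartem or another local standard antimalarial "will be administered on Day 29 in all patients in Part A of the study". A patient given such a drug earlier because of treatment failure does not need the Day 29 course. On follow-up, Protocol 3.1 states: "A safety follow-up call will be performed on Day 31 for Part A". Protocol 8.6.1 sets AE monitoring at a minimum of 30 days after the last dose, or longer if five half-lives or the end-of-study visit falls later.

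In Part B, Protocol 6.8.3 allows Coartem or another local antimalarial as rescue for failures in the combination arm, and calls for an alternative in the Coartem arm. Protocol 12.3.7 (Cohort B2) also sends a combination-arm patient who vomits the replacement dose to Coartem or another suitable rescue drug.

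**The concern.** The safety objective is the tolerability of each agent as monotherapy (Part A) and of the combination against standard of care (Part B). A period that never closes mixes the effects of two drugs under one treatment label.

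Two features make this more than a labelling matter. First, Part A has no control arm, so nothing in the tables shows how much of an arm's incidence belongs to the second drug. Second, early rescue is triggered by treatment failure, so the amount of second-drug follow-up is tied to efficacy and, through it, to dose. In Part B the comparator can itself be the rescue drug, so an event caused by Coartem can be counted against the combination.

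The SAP deals with rescue on the efficacy side: it resets PCT in Part A (2.5.3) and treats non-study antimalarials by a composite strategy for uncorrected ACPR (1.2.3). The visible safety sections have no counterpart. The footnote to SAP Table 5-6 also restricts the Part A non-study antimalarial category to Coartem taken before the Day 29 visit. The scheduled Day 29 course therefore falls outside that summary, while events after it still enter the AE tables.

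**Working it through.** The plan gives no figure for this overlap, so there is none to reproduce. The check is a day count.

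**Inputs from the documents**
- Dosing on Day 1 (Protocol 6.1.3; SAP 2.1.1).
- Second antimalarial on Day 29 for all Part A patients not already rescued (Protocol 6.8.3 and 6.6).
- Last planned Part A safety contact on Day 31 (Protocol 3.1).

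**Assumptions**
- Follow-up ends on Day 31. It is longer if five half-lives or the end-of-study visit is later; no half-life is visible.
- The rescue days and failure fractions below are illustrative.

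**Per patient.** For a second antimalarial starting on day s, the share of days on or after it is (31 − s + 1)/31, counting the start day. The days before it are s − 1.

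| Start day s | Days on or after | Share | Days before | Share |
|---|---|---|---|---|
| 4 | 28 | 90.3% | 3 | 9.7% |
| 8 | 24 | 77.4% | 7 | 22.6% |
| 15 | 17 | 54.8% | 14 | 45.2% |
| 22 | 10 | 32.3% | 21 | 67.7% |
| 29 (no failure) | 3 | 9.7% | 28 | 90.3% |

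Counting only days strictly after Day 29, the non-failure share is 2/31 = 6.5%.

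**Per arm.** With a fraction f rescued on day r and the rest treated on Day 29, the share is [f(31 − r + 1) + (1 − f) × 3]/31.
- r = 15, f = 0: 3/31 = 9.7%.
- r = 15, f = 0.1: (1.7 + 2.7)/31 = 14.2%.
- r = 15, f = 0.3: (5.1 + 2.1)/31 = 23.2%.
- r = 15, f = 0.5: (8.5 + 1.5)/31 = 32.3%.
- f = 0.3, with r from 22 to 8: (3.0 + 2.1)/31 = 16.5% to (7.2 + 2.1)/31 = 30.0%.

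For any r before 29 the share rises with f, so the direction does not depend on the values chosen.

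**Which tables are affected.** For a patient rescued early, later AEs, laboratory values, ECGs and vital signs can all fall after the second drug. For a patient without failure, Protocol section 8 places the end-of-study visit on Day 29 and the Day 31 contact is a call. Scheduled laboratory and ECG data are then affected only if they are taken after dosing on Day 29. Table 8-1, which would show the order, is redacted.

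**The case against.** The strongest reply is that counting every event after first dose is a recognised treatment-policy summary, that the SAP implements Protocol 9.4.2 faithfully, and that late events of a single-dose drug are of real interest. That stands, and the all-post-dose tables should stay. What is missing is a companion view.

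A second reply is that cutting the main tables at rescue would bring its own bias: failing arms would be observed for less time and could look safer. A Day 4 rescue would leave 3 of 31 days. This also stands, and it rules out simply replacing the main definition.

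Third, partial handling exists. Investigators assess causality, treatment-related AEs are tabulated separately (SAP 2.7.1), rescue date and time are recorded (Protocol 6.8.3), and listings carry study day. This makes post-rescue events traceable. It does not correct the all-AE, worst-laboratory or notable ECG and vital-sign tables, and causality is judged open-label.

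A reader might infer a specific spurious AE difference between doses. Suppose 20% of rescue courses cause a new AE, and 50% of one arm but 5% of another are rescued: that gives 0.20 × (0.50 − 0.05) = 9 points. The documents supply none of these inputs. The sum also ignores that patients without failure receive the Day 29 course. If a share q of second-drug AEs appears by Day 31, the gap is 9(1 − q) points: 4.5 at q = 0.5, and near zero as q nears 1. Patients who already had an AE would shrink it further.

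A reader might also infer that Part B dose selection is misled. That is not shown: the sponsor and DMC review safety, efficacy and PK data (Protocol 3.1, 6.5 and 9.7), the team may see individual data (6.3.2), and the criteria in 6.5.2 are redacted.

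**Conclusion.** The point holds as a gap in the safety reporting, and it is cheap to close. As written, the Part A safety tables attribute some post-rescue findings to the investigational dose, and the share of follow-up affected rises as efficacy falls. The same mechanism can place rescue-drug events, including those of Coartem, in the Part B combination arm.

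The size that can be stated is time, not incidence: about 90%, 55% or 32% of Days 1 to 31 for a rescue on Day 4, 15 or 22, against about 10% without failure. The effect on AE rates cannot be derived from the documents.

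It would overstate the case to say that every Part A patient's safety record is materially contaminated. Without failure the overlap is two to three days and concerns mainly AEs, and patients lost before Day 29 may never receive the course.

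The conclusion rests on visible text. The SAP follows protocol version 03 of 20-Mar-2024, whereas the protocol supplied is Amendment 2 of June 2023. SAP section 4 and other blocks are redacted, and the table shells were not supplied. An unseen rule that splits or flags these data cannot be excluded. Part C appears only in the SAP, so its rescue rules could not be checked.

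**What to change.** 1. Keep the all-post-dose tables as Protocol 9.4.2 specifies.
2. In SAP 2.1.1, define a cut date: the start of the first non-study antimalarial, whether rescue, other concomitant use, or the scheduled Part A Day 29 course. For this purpose the restriction in the Table 5-6 footnote should not apply. State how same-day events and partial dates are assigned.
3. In SAP 2.7, add a companion set restricted to data before the cut date: AE incidence, worst post-baseline laboratory values, and notable ECG and vital-sign values. Report time at risk by arm beside it, because the truncation depends on efficacy.
4. Flag events starting on or after the cut date and tabulate them separately by the drug given.
5. Keep deaths and SAEs over full follow-up.

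The cost is SAP wording and one extra set of tables. Rescue dates and times are already required in the record. The downside is shorter, efficacy-dependent follow-up in the companion set, so it should be read alongside the main tables and not in their place. This changes reporting only; no rescue, Day 29 or other clinical rule is altered.
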